#### *In-Person Eligibility Confirmation:*

Veterans who meet all inclusion/exclusion criteria throughout the phone screening process will be consented for participation and proceed to in-person eligibility confirmation. The final screening step involves in-person testing at Hines VA to confirm that cognitive impairments are moderately impaired in capacity and function as determined by a battery of clinician rated tests including RBANS, WAIS-V, DKEFS, BRIEF, Dot Counting Test and AMPS. We measure cognitive capacity according to neuropsychological tests that correlate with functional

disability. We developed a testing battery that can be used to determine study eligibility and that can be feasibly repeated to use as an outcome indicative of persisting cognitive gains (Table 2). The Audit C and DAST-10 will be completed at this time.

*Alcohol and Substance Use:* As part of eligibility screening, during the in-person screening, the participant will complete the following two self-report tests:

The AUDIT-C is a brief alcohol screening instrument that identifies persons who likely to be hazardous drinkers or have active AUD (including alcohol abuse or dependence). The AUDIT-C has 3 questions and is scored on a scale of 0-12. Each AUDIT-C question has 5 answer choices valued from 0 points to 4 points. In men, a score of 4 or more is considered positive, optimal for identifying hazardous drinking or active alcohol use disorders. In women, a score of 3 or more is considered positive. Generally, the higher the score, the more likely it is that a person's drinking is affecting his or her safety.

The DAST, a NIDA CTN common data element, is a brief, self-report instrument for population screening, clinical case finding and treatment evaluation research. The DAST-10 is a 10-item self-report instrument that has been condensed from the 28-item DAST. Scores range from 0 to 10 with scores of 1-2 being considered low level problems that should be monitored with re-assessments periodically whereas further evaluation is indicated with a score of 3 or more.

Persons with alcohol use disorder (AUD) and/or substance use disorder (SUD) diagnoses confirmed by clinical and/or scientific experts (e.g., Research Neuropsychiatrist [name], Neuropsychologist [name], Neurologist/Epileptologist [name]) and/or scientific subject matter expert (e.g., [name]) will be excluded.

[figure not shown]
Persons who do not have AUD or SUD but do consume alcohol and/or use illicit substances at a level, as determined by clinical and/or scientific experts (e.g., Research Neuropsychiatrist [name], Neuropsychologist [name], Neurologist/Epileptologist [name]) and/or scientific subject matter expert (e.g., [name]), likely to elevate seizure risk (i.e., hazardous level plausibly lowering of seizure threshold) will be excluded.

If a participant screens positive on the AUDIT-C (Men score of 4 or more, women score of 3 or more), then they will be referred to their clinical care team for further evaluation and clinical management.

If a participant scores 1 to 2 on the DAST, then substance use will be monitored by having researchers re-administer the DAST on each study day.

[figure not shown]
If at any time a participant scores a 3 or more on the DAST, then they will be referred to their clinical care team for further evaluation and clinical management.

**Figure 1. Four Step Screening Process: Summary of Exclusion Criteria by Steps**

For this within-subject placebo-controlled partially-blinded treatment protocol (Fig 2), we will enroll 48 medically stable Veterans with stabilized recovery trajectories after a stroke or a TBI and who have a homogeneous level of moderately impaired cognitive function persisting after standard rehabilitation.

An equal number of Veterans with stroke/TBI (24-stroke; 24-TBI) will be enrolled, but we will over-sample females (Figure 2). For each iTBS group to include an equal number of Veterans with stroke/TBI, Veterans will be randomly assigned by diagnostic groups, to receive Active iTBS or Placebo iTBS. To measure immediate effects (ImE), an equal number of Veterans with stroke/TBI within each iTBS group will be randomly assigned to be tested with the Modified Digit Span (MDS) or AMPS, three times at 30 min intervals. Persisting effects (PE) tests will be administered to all participants at five timepoints including prior to and after Active iTBS or Placebo iTBS and 2-weeks later prior to the 2nd intervention, where all Veterans receive APT paired with their assigned iTBS (Active iTBS + APT or Placebo iTBS + APT). The alternate ImE test is then administered three times at 30 min intervals, followed by re-administration of all PE tests. Two weeks later, all PE tests are administered a 5th time (B4). ImE and PE measures are used to define magnitude and duration of cognitive change. Randomization (SAS Proc Plan) will be managed by one un-blinded researcher who will not provide interventions or conduct testing.

**Figure 2. Study Design (ImE = Immediate Effects Tests; AMPS = AMPS or MDS = Modified Digit Span; PE = Persisting Effects Tests for all participants; Study Day-1: Obtain Covariates and Treatment preparation information; B0 = Pre-Study-Day-2; B1 = Post-Study-Day-2; After 2-Weeks B2 = Pre-Study-Day-3; B3 = Post-Study-Day-3; After 2-Weeks B4 = Study-Day 4)**

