## Abstract

The purpose of this SPiRE is to identify the supports and barriers to scalability of Veteran-tailored iTBS and APT across neurologic conditions, with the longer-term goal of providing an empirical basis for the tailoring of a broader range of cognitive rehabilitation strategies to optimize each Veteran's cognitive function in daily life. After Veterans receive standard cognitive rehabilitation, cognitive impairments often persist and if they do make gains there is limited carry-over to daily function. The tenets of precision neurorehabilitation suggest that tailored interventions will optimize gains and carry-over, but precision-tailoring of cognitive rehabilitation will only be possible if researchers develop and test scalable approaches for identifying, organizing, and analyzing the multitude of Veteran-specific variables driving and influencing treatment responsiveness. This project addresses long-standing scientific barriers to understanding treatment responsiveness, particularly study sample heterogeneity and individual variability. We address study sample heterogeneity by linking Veterans, across TBI and ischemic stroke, according to levels of cognitive impairment. We create a cohort of Veterans with a homogeneous level of cognitive impairment, thereby enabling explication of person-centric factors influencing treatment responsiveness and carry-over to daily function. Advancing understanding of the basic study design elements will be achieved by leveraging our knowledge of intermittent Theta Burst Stimulation (iTBS) and iTBS paired with Attention Processing Training exercises (iTBS + APT). iTBS is advantageous as it robustly improves working memory with just one treatment session. These interventions, together, are advantageous as they can each be tailored to a Veteran's unique cognitive challenges and to target the neural site, unique to each Veteran's neuropathology. These two interventions also directly address cognitive deficits, while simultaneously inducing neuroplasticity in neural regions hampered or impaired by neural injury. We will study Veterans with moderately impaired cognition who, after standard cognitive rehabilitation, continue to struggle with daily life requiring assistance with complex instrumental activities of daily living (IADL). Veterans will participate in a series of two within-subject treatment studies, conducted on two separate days, 2-weeks apart. Veterans will be randomly assigned to first receive a single session of Active iTBS or Placebo iTBS and then they will receive APT paired with their assigned iTBS (Active iTBS + APT vs Placebo iTBS + APT). We will test if diagnosis moderates the effects of these interventions on both immediate and persisting change in cognition. For immediate effects, we use a novel testing battery and for persisting gains we use established and feasible neuropsychological tests as well as an established test of cognitive function during IADL. Results will be used to obtain pilot data and examine feasibility in terms of study attrition relative to Veteran fatigue, mood, and Veteran reports of suitability of key aspects of the study design. These findings will be used to develop a future merit within-subject cross-over study examining the overarching hypothesis that tailored iTBS and APT applied to a transdiagnostic sample and subsequently matched to a Veteran, according to a biotype algorithm, will result in better functional performance of Veteran-valued IADL.

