### 3.0 Objectives

**Aim 1: Elucidate merits of transdiagnostic sampling.** Within the two intervention groups (Group 1: n = 24, Active iTBS and Active iTBS + APT; Group 2: n = 24, Placebo iTBS and Placebo iTBS + APT), we expect that (1i) neurologic diagnosis (stroke, TBI) will not moderate the effect of Active iTBS or Active iTBS + APT on Maximum Cognitive Gain as assessed by the Modified Digit Span (MDS) and the Streamlined AMPS (AMPS).

**Aim 2: Obtain pilot data to inform estimation of treatment and practice effects.** We will gather pilot data regarding the magnitude and duration of treatment effects as well as MDS and AMPS practice effects. As we anticipate (2i) greater immediate gains in IADL performance (AMPS) after Active iTBS + APT when compared to Active iTBS alone, we will compare Maximum Cognitive Gains (MCG) on MDS with MCG on AMPS between the Active iTBS and Active iTBS + APT groups to determine if MCGs differ in magnitude. We will also determine if

Active iTBS + APT trend lines indicate an additive treatment effect of APT on MDS and/or AMPS. We also anticipate (2ii) some persisting treatment effects and to explicate these effects we will examine effects for Active iTBS and Active iTBS + APT in the short-term (post-pre-treatment), long-term (2 weeks after a session) and cumulatively across treatment sessions. Since the AMPS uses a unique task during each testing interval and MDS uses 1 of 6 alternate test forms, we will determine (2iii) presence and magnitude of practice effects by testing whether prior exposure to MDS or AMPS results in MDS or AMPS gains for Placebo iTBS.

**Aim 3: Explicate study attrition by perceived suitability of aspects the study design and the relationship between this perceived suitability and fatigue as well as mood.** We will test the ideas that (3i) Attrition rates do not differ by stroke and TBI groups, (3ii) Veterans across stroke and TBI have similar perceptions regarding suitability of the number and type of tests as well as number of study-days, and (3iii) perceived suitability is related to Veteran-reported fatigue and mood.

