**Study-Day 2 (4 days after Study Day 1)(~8 hours):**

- 1. PE testing battery
- 2. A single session of **Active** iTBS or **Placebo** iTBS
- 3. Randomly assigned ImE test (MDS or AMPS), administered 3-times at 30 min intervals, each interval includes 5 to 15 min of rest).
- 4. PE testing battery
- 5. Suitability ratings 1-3

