**Study-Day 3 (2 weeks after Study Day 2)(~8 hours):**

- 1. PE testing battery
- 2. Single session **Active** iTBS+ APT or **Placebo** iTBS+APT
- 3. Alternate ImE test (MDS or AMPS) three times at 30min intervals
- 4. PE testing battery
- 5. Suitability ratings 1-3

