## 5.6 Data Analysis

**Sample Size to Estimate Effect Sizes.** Our total sample size of 48 participants is based on 80% power to detect an Effect Size (ES) of .90. For 80% power, sample size per group to detect a small ES (0.35) is 130, for a medium ES (0.60) it is 42 and to detect a large ES (0.90) it is 21 per group. To estimate a large ES of 0.90, 42 subjects are required to achieve 80% power. Thus, we plan for 48 participants and 12% attrition.

Published methods  will be used to examine the merits of transdiagnostic sampling (Aim 1i). Specifically, we will use MLM to determine if neurologic diagnosis (stroke, TBI) moderates the effects of the Active intervention (Group 1: n = 24, Active iTBS and Active iTBS + APT; Group 2: n = 24, Placebo iTBS and Placebo iTBS + APT) on Maximum Cognitive Gain (MCG) as measured with the MDS and the AMPS.

For Aim 2, we will inform estimates of effect sizes by testing the idea (2i) that MDS gains and AMPS gains differ for Active iTBS and Active iTBS + APT. As specified in Table 1, we will examine if gains differ in magnitude by computing the MCGs for each outcome (MDS and AMPS) by each intervention. For each outcome, we will compare the Average Active iTBS MCG with the Average Placebo iTBS MCG and the Average Active iTBS + APT MCG with the

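### No Veteran has the same immediate-effect test series after iTBS and after iTBS + APT, so the 2i contrast of the two interventions is between different Veterans, and the tests in Section 5.6 cannot show what APT adds

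*Combined protocol and SAP*

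**What the plan says.** The Abstract describes the study thus: "Veterans will participate in a series of two within-subject treatment studies". Section 5.1 repeats the label: "For this within-subject placebo-controlled partially-blinded treatment protocol (Fig 2), we will enroll 48 medically stable Veterans". A Veteran keeps the same stimulation arm on both treatment days (Section 5.6: "Group 1: n = 24, Active iTBS and Active iTBS + APT", with a Placebo group of the same size).

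Within each arm, balanced by diagnosis, Veterans "will be randomly assigned to be tested with the Modified Digit Span (MDS) or AMPS". The Study-Day 2 list gives "Randomly assigned ImE test (MDS or AMPS), administered 3-times at 30 min intervals" after iTBS alone. The Study-Day 3 list gives "Alternate ImE test (MDS or AMPS) three times at 30min intervals" after iTBS + APT. The design text in Section 5.1 says the same of the second session: "The alternate ImE test is then administered three times at 30 min intervals, followed by re-administration of all PE tests". Table 2 in Section 5.5 shows three repetitions for each ImE test, which fits one series of each per Veteran.

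Aim 2 in Section 3.0 anticipates "greater immediate gains in IADL performance (AMPS) after Active iTBS + APT when compared to Active iTBS alone". For 2i, Section 5.6 specifies t-tests of Maximum Cognitive Gain (MCG), Active against Placebo for each outcome and each intervention, and group-by-time terms that are also Active against Placebo within a session.

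The PE battery is given to all Veterans before and after both sessions (B0 to B3) and again at B4. It contains AMPS and WAIS-IV Digit Span but not MDS. Section 5.6 uses PE measures for 2ii, as Active against Placebo.

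**The concern.** Hypothesis 2i sets one intervention against another, and the same 24 Active Veterans receive both. Because the ImE test switches between days, a Veteran's two ImE results differ in test and in intervention together. For a single ImE test, the two interventions are seen in different people, and stable differences between people stay in the error.

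The specified tests do not fill the gap. On Day 3 both arms have APT, so Active iTBS + APT against Placebo iTBS + APT isolates stimulation, not APT. The protocol wants to know whether trend lines indicate an additive effect of APT, and this comparison cannot tell it. The pilot is meant to inform later within-subject cross-over studies, so a cross-session estimate, with an honest label and standard error, is one of the things it should deliver.

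**Working it through.** **Inputs**
- Arms of 24 and 24, same arm on both days (Sections 3.0 and 5.6).
- About 12 MDS-first and 12 AMPS-first per arm: inferred from the balanced random assignment in Section 5.1, not stated.
- Effect size 0.90, 80% power, 21 per group, 48 enrolled for 12% attrition (Section 5.6). Alpha is not stated for this calculation; two-sided 0.05 is assumed.
- Correlation ρ between a Veteran's Day 2 gain and Day 3 gain: not in the documents. Values 0, 0.3 and 0.5 are assumed.

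**1. The plan's own figure.** A two-sample t-test at effect size 0.90 needs 21 per group (power 81%), and 42/0.88 = 47.7, so 48. This reproduces.

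**2. Who contributes, Active arm**

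| Veterans | Day 2, iTBS | Day 3, iTBS + APT |
|---|---|---|
| about 12 | MDS series | AMPS series |
| the other 12 or so | AMPS series | MDS series |
| all 24 | PE AMPS and Digit Span, B0 and B1 | PE AMPS and Digit Span, B2 and B3 |

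The sample-size paragraph does not name its comparison. If 0.90 is applied to one ImE test, 12 v 12 has 56% power, and about 10.5 v 10.5 after attrition has 50%.

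**3. What each contrast estimates.** Let p1 and p2 be the session and practice gains on Days 2 and 3, a the effect of APT common to both arms, and t1 and t2 the iTBS effects on the two days.
- Day 2 mean gains: Placebo p1; Active p1 + t1.
- Day 3 mean gains: Placebo p2 + a; Active p2 + a + t2.
- Active minus Placebo on Day 3 = t2. The APT term cancels.
- Day 3 minus Day 2, Active arm = (p2 − p1) + a + (t2 − t1).
- Day 3 minus Day 2, Placebo arm = (p2 − p1) + a.
- Difference between arms = t2 − t1.

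Only the cross-session contrasts contain a, and there it is mixed with practice and order.

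**4. Standard errors, in each measure's own gain-SD units**
- Unpaired ImE contrast in the Active arm: √(2/12) = 0.41.
- Paired PE contrast (B3−B2) − (B1−B0), one arm: √(2(1−ρ)/24).
- Between-arm difference of that contrast: √2 times the one-arm value.

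| ρ (assumed) | One arm, 24 paired | Between arms |
|---|---|---|
| 0 | 0.29 | 0.41 |
| 0.3 | 0.24 | 0.34 |
| 0.5 | 0.20 | 0.29 |

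The corresponding between-arm difference from unpaired ImE data, with four cells of 12, is √(4/12) = 0.58.

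**The case against.** Several parts of the opposing case stand.

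- A reader might infer that no Veteran has any test in common across the two interventions. That is not so: every Veteran has AMPS and WAIS-IV Digit Span at B0 to B3. Only the ImE series, and MDS as an instrument, are not repeated.
- A reader might infer that the protocol promised a within-subject test for 2i and then lost it. The label belongs to the protocol as a whole. Aim 2 speaks of groups, and Section 5.6 plans no paired test of iTBS against iTBS + APT.
- It is tempting to read the standard errors as a precision gain of 29% to 50%. The documents do not support that. The ratio requires equal gain SDs for a maximum over three immediate tests and for a single later change, and ρ is not given. At ρ = 0 the whole reduction comes from using 24 Veterans instead of 12 per side, not from pairing. A negative ρ is possible: at −0.3 the one-arm value is √(2.6/24) = 0.33.
- It is also tempting to make the PE contrast the main 2i estimate. Hypothesis 2i concerns immediate gains, and the ImE tests exist to capture them. The post-session PE tests come after three ImE administrations. Table 2 allows 1.5 hours for each AMPS and 0.2 hours for each MDS, so delay and prior AMPS exposure before B1 and B3 depend on ImE order.
- The text does not make clear which assessments form the MCG. Section 5.6 refers to Table 1, which is the eligibility table, and no ImE test is listed before stimulation. An AMPS gain may already use B0 or B2 as its starting value.

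None of this restores the same ImE series on both days, or lets an Active-against-Placebo test within Day 3 show an effect that both arms share.

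**Conclusion.** The point holds in limited form. On MDS or on ImE AMPS, any contrast of iTBS with iTBS + APT is between about 12 and about 12 different Active Veterans, and the tests specified for 2i cannot show an additive effect of APT. Data for a paired estimate in all 48 Veterans are already collected but not assigned to 2i.

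The figures rest on an even split of ImE order, assumed values of ρ and full follow-up, and they are not comparable across measures as effect sizes. This is an inexpensive improvement to a pilot, not a fault that invalidates it. The paired contrast supports the ImE analysis and does not isolate APT: in one arm APT remains confounded with practice and carry-over, and the between-arm difference concerns iTBS.

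**What to change.** In Section 5.6:

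1. Keep the ImE analysis for 2i, and state that its iTBS against iTBS + APT contrast on a given test is between different Veterans.
2. Add a pre-specified supporting contrast, (B3−B2) minus (B1−B0), on PE AMPS and on WAIS-IV Digit Span. Estimate it in the 24 Active Veterans, in the 24 Placebo Veterans and as the difference between arms, with ImE test order as a factor, and report confidence intervals.
3. State the limits:
   - The PE post-test is later than the ImE tests and follows a different test load according to ImE order.
   - iTBS always precedes iTBS + APT, so the single-arm contrast confounds APT with practice and carry-over.
   - The between-arm difference estimates the change in the iTBS effect when APT is added, not the effect of APT itself.
4. State that Active against Placebo on Day 3 does not test an additive effect of APT.

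The cost is SAP wording and a few more estimates within the false-discovery-rate control already planned for Aim 2. No visit, test or participant is added.

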### Study-Day 0 (In Person Eligibility Screening) (2-3 hours)

1. Complete questionnaires and testing
  - a. Audit-C and DAST-10

- b. Testing questionnaires
- c. Demographic information collection

**Study-Day 1 (~5 hours) (may occur over 2 days):**

- 1. Complete tests/questionnaires that are not repeated. Some are collected for use as covariates (Table 2) and some are needed for treatment preparation.
  - a. Baseline testing battery
  - b. APT Baseline
  - c. fMRI-to be completed at NU CTI
  - d. Motor Threshold
  - e. Baseline EEG\*
- 2. Rating suitability of the number and types of tests 1-3.

\*EEG to be completed prior and reviewed by physician prior to Motor Threshold

**Study-Day 2 (4 days after Study Day 1)(~8 hours):**

- 1. PE testing battery
- 2. A single session of **Active** iTBS or **Placebo** iTBS
- 3. Randomly assigned ImE test (MDS or AMPS), administered 3-times at 30 min intervals, each interval includes 5 to 15 min of rest).
- 4. PE testing battery
- 5. Suitability ratings 1-3

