**Study-Day 4 (2 weeks after Study-Day 3) (~2.5 hours):**

[figure not shown]
- 1. PE testing battery
- 2. Suitability rating 1-8

**Optional Study for Participants with diagnosis of TBI only- Day 5 (to occur within 2 weeks of Day 4, can occur on same day as Day 4) (~2 hours)**

- 1. Single session of Active iTBS at GIMME site of stimulation
- 2. ImE test: MDS, one time only
- 3. ImE test: AMPS, one time only

### Figure 3. Study Procedures by Study-Days 1 thru 4

ImE = Immediate Effects Tests; s-AMPS = Streamlined AMPS or MDS = Modified Digit Span; PE = Persisting Effects Tests for all participants

**Interventions.** All iTBS sessions will be **double-blinded**, but APT exercises **will not be blinded**. For **Active** iTBS and **Placebo** iTBS, the left DLPFC using the Resting Network Mapping algorithm.

**fMRI (neuroimaging)-** Functional MRI (fMRI) measures will be collected at Baseline. The fMRI measures will include structural imaging, 20 minutes of resting-state fMRI, diffusion tensor imaging (DTI) and an Arterial Spin Labelling Sequence (ASL). Participants will be in the MRI for approximately 55 minutes. fMRI scanning, for all participants, will take place at Northwestern University's CTI in the Olsen Pavilion located at [name].

Veterans will be responsible for transportation to the CTI, however parking vouchers will be provided at no cost to the participant. Parking is available at the Northwestern Memorial Hospital parking garage located across from the Olsen Pavilion. Research staff will be present on day of scan and available to provide assistance.

Scanning will take place on a Siemens Prisma 3.0 T MRI scanner equipped with a 64-channel head/neck coil. A high-resolution 3D MP-RAGE T1-weighted sagittal anatomical scan (voxel size = 0.8 mm isotropic resolution; 224 sagittal slices) will be collected for each participant. Resting state BOLD data will be collected using T2\* weighted EPI with a TR=0.5s, TE=25ms, flip angle of 48°, and 2mm isotropic voxels and a multiband factor of 8. Rest data will be collected while the subject views a fixation crosshair. The DTI data will use a two shell (64 directions per shell) acquisition with diffusion values of 1000 mm^2/sec. The acquisition will collect 1.5mm isotropic voxels with a TR=4500, TE=62ms and a multiband factor of 4, and 96 slices.

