For measuring immediate changes in cognitive function, we will use the aforementioned **AMPS**. For each of the *three administrations, in 30-min intervals*, a unique task will be randomly selected (without replacement) from the set of tasks developed during Step 4 (Fig 1). Thus, the same IADL is never repeated for the same Veteran.

**Persisting Effects (PE) Measures.** This battery includes the same five tests/sub-tests administered during screening (Fig 1, Step-4: AMPS, RBANS, WAIS-IV Digit Span, DKEFS subtests and BRIEF-A). As the BRIEF-A will be re-administered, the study Neuropsychologist will review BRIEF-A scores and, if there are compelling reasons, Veterans with scores suggesting atypical validity will be withdrawn. This battery also includes tests to measure change in mood: Columbia Suicide Severity Rating Scale (C-SSRS) *Beck Anxiety Inventory (BAI)*, and the *Posttraumatic Stress Disorder Checklist (PCL)*. To assess fatigue, we will use the Fatigue Severity Scale (FSS), which is a self-report measure of prior-week fatigue during nine activities and current fatigue. To measure behavioral features of agitation, we will use the *Agitated Behavioral Scale (ABS)*.

Table 2: Instrumentation: Testing Battery					
Immediate Outcome Effects (ImE)	Hrs/Admin	Aims	Variable Types	# Reps	
AMPS	1.5	1 & 2	Continuous (logit)	3	
Modified Digit Span (MDS)	0.2	1 & 2	Proportional (% correct)	3	
Persisting Effects Testing Battery (PE)	Hrs/Admin	Aims	Variable Types	# Reps	
Repeatable Battery for Assessment of Neuropsych Status (RBANS)	1.0	2	Continuous (normed score)	5	
Weschler Adult Intelligence Scale (WAIS-IV) Digit Span			Proportional (% correct)	5	
Delis-Kaplan Executive Functioning System (DKEFS): Color-Word			Continuous (normed score)	5	
Behavior Rating Inventory of Executive Function (BRIEF)			Continuous (normed score)	5	
AMPS	1.5	2	Continuous (logit)	5	
PTSD Checklist (PCL)	0.1	2 & 3	Mean # symptoms/ severity	5	
Columbia Suicide Severity Rating Scale (C-SSRS)	0.1	2 & 3	Raw score (Veteran rating)	5	
Beck Anxiety Inventory (BAI)	0.1	2 & 3	Raw score (Veteran rating)	5	
Agitated Behavior Scale (ABS)	0.1	2 & 3	Raw score (research clinician rating)	5	
Fatigue Severity Scale (FSS): Prior Week Daily Living Score	0.1	2 & 3	Raw score (Veteran rating)	5	
Fatigue Severity Scale (FSS) L VASF Current Fatigue Rating	0.1	2 & 3	Raw score (Veteran rating)	5	

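### AMPS at the listed 1.5 h per administration cannot satisfy both the 30-minute immediate-effects schedule and the roughly 8-hour study day

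*Combined protocol and SAP*

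**What the plan says.** **Schedule (section 5.1).** On Study-Day 2 the randomly assigned ImE test is "administered 3-times at 30 min intervals, each interval includes 5 to 15 min of rest". Study-Day 3 has "Alternate ImE test (MDS or AMPS) three times at 30min intervals". A PE battery that itself contains AMPS is given before and after on both days. Each of these days is stated as about 8 hours. Study-Day 4 is one PE battery plus suitability ratings: "Study-Day 4 (2 weeks after Study-Day 3) (~2.5 hours".

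**AMPS by name (section 5.5, Immediate Effects Measures).** The interval is applied to AMPS specifically: "three administrations, in 30-min intervals", each with a different task.

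**Test times (section 5.5, "Table 2: Instrumentation: Testing Battery").** The time column is headed as hours per administration. The rows read:
- ImE: "AMPS 1.5 1 & 2 Continuous (logit) 3"
- ImE: "Modified Digit Span (MDS) 0.2 1 & 2 Proportional (% correct) 3"
- PE: "AMPS 1.5 2 Continuous (logit) 5"

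**Analysis (section 5.6).** Trends in ImE outcomes are examined through a group-by-time interaction. The section does not say whether time means test order, nominal minutes or actual minutes.

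**The concern.** A 30-minute interval that includes 5 to 15 minutes of rest leaves 15 to 25 minutes for a test listed at 90 minutes. Three such tests, added to two PE batteries that each contain a further AMPS, do not fit in about 8 hours.

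Time since stimulation matters here because Aim 2 sets out to estimate both the magnitude and the duration of effects. If AMPS takes as long as Table 2 says, the immediate window is several hours for AMPS and about an hour and a half for MDS. The Aim 2i comparison of MDS gains with AMPS gains would then mix the outcome with time since iTBS. The post-session PE batteries (B1, B3) would also start hours later for participants who had AMPS that day. A longer day bears on fatigue, perceived suitability and attrition, which Aim 3 studies.

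**Working it through.** **Inputs**
- AMPS 1.5 h, MDS 0.2 h (Table 2).
- Neuropsychological part of the PE battery: 1.0 h. The entry stands beside RBANS, and the cells for Digit Span, DKEFS and BRIEF are blank. It is read here as covering all four tests, the reading that gives the shortest day.
- Six short PE scales at 0.1 h each (Table 2).
- APT on Day 3: 30 + 10 + 5 = 45 min = 0.75 h (section 5.1, Interventions).
- iTBS, set-up, meals and ratings: counted as zero.

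**PE battery** = 1.0 + 1.5 + 6 × 0.1 = 3.1 h, so two batteries = 6.2 h.

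**Can the stated 8 h be reproduced with AMPS as the ImE test?** No.
- AMPS back to back: 3 × 1.5 = 4.5 h. Day 2 = 6.2 + 4.5 = 10.7 h. Day 3 = 10.7 + 0.75 = 11.45 h.
- With 5 to 15 min of rest per administration, the block is 4.75 to 5.25 h. Day 2 = 10.95 to 11.45 h.
- AMPS alone is given five times that day: 5 × 1.5 = 7.5 h.

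**With MDS as the ImE test?** Yes.
- 12 min of testing plus 5 to 15 min of rest = 17 to 27 min, which fits a 30-min interval.
- The block is 3 × 0.2 = 0.6 h of testing, or 1.5 h as three 30-min slots.
- Day 2 = 6.8 to 7.7 h. Day 3 = 7.55 to 8.45 h.

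**Optional Day 5** = 1.5 + 0.2 = 1.7 h plus iTBS, against about 2 h. This fits.

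**Day 4** = 3.1 h against about 2.5 h.

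**Other readings of the AMPS figures**

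| Reading | Day 2 | Day 3 | Consequence |
|---|---|---|---|
| 30 min is the gap from the end of one test to the start of the next (3 × 1.5 + 2 × 0.5 = 5.5 h) | 11.7 h | 12.45 h | Interval conflict goes; overrun grows |
| Each ImE AMPS fits a 30-min slot, PE AMPS stays 1.5 h (block 1.5 h) | 7.7 h | 8.45 h | Days fit; the ImE entry in Table 2 is wrong |
| Every AMPS takes 0.5 h (PE battery 2.1 h) | 5.7 h | 6.45 h | Both AMPS entries are wrong; Day 4 = 2.1 h |

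**Timing after stimulation on Day 2, first test starting at once.** On the gap reading the third AMPS starts at 1.5 + 0.5 + 1.5 + 0.5 = 4 h. The third MDS starts at about 1 h with 30 min from start to start, or 0.2 + 0.5 + 0.2 + 0.5 = 1.4 h on the gap reading. With AMPS back to back, B1 starts 4.5 − 1.5 = 3 h later for AMPS than for MDS in three 30-min slots.

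**The case against.** The strongest reply is that one table cell is wrong. The streamlined AMPS uses a single task, and 1.5 h equals 3 × 0.5 h, so the ImE entry may be a total for three short administrations. The days then come to 7.7 h and 8.45 h, close to what is stated. This is plausible, and it makes the 10.7 h and 11.45 h figures conditional on that cell. It is not established. The column is per administration, the PE row gives the same 1.5 h for one administration, the MDS entry reads as one test, and the stated length of Day 5 suits one 1.5 h AMPS. No section gives a shorter time for the streamlined form. If the reply is right, Table 2 still needs correcting.

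A second reply is that 30 minutes may be the gap between tests. That removes the interval conflict, but at 1.5 h per AMPS it lengthens the day.

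Three stronger inferences are tempting, and the documents do not support them:
- *The active-versus-placebo contrasts are biased.* Section 5.1 randomises equal numbers of stroke and TBI participants within each iTBS group to MDS or AMPS first, so differences in lag are balanced between arms by design.
- *The trend models wrongly assume 30-minute spacing.* Section 5.6 does not define time, so the plan leaves a gap and states no wrong assumption. Nor does it tie Maximum Cognitive Gain to clock time.
- *No study day can be met as stated.* MDS days and optional Day 5 fit. Each participant has one affected long day.

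The Day 4 mismatch is also weak. It is 0.6 h against an approximate figure, it equals the six 0.1 h scales, and it rests on how the 1.0 h entry is read.

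**Conclusion.** The schedule is inconsistent as written. If 1.5 h is the time for one AMPS, no reading satisfies both the 30-minute interval and the 8-hour day. The overrun on the one affected day is at least 10.7 − 8 = 2.7 h (Day 2) or 11.45 − 8 = 3.45 h (Day 3), with everything other than testing and APT counted as zero. A longer neuropsychological time than 1.0 h would only add to it. If each ImE AMPS really takes about 30 minutes, the overrun essentially disappears and Table 2 is in error. The documents do not show which figure is wrong.

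The consequences are for the estimate of effect duration, the MDS-versus-AMPS comparison in Aim 2i, the precision of B1 and B3, and the participant burden behind the Aim 3 outcomes. The validity of the randomised active-versus-placebo comparison is not in question. Day 4 is a secondary, approximate mismatch.

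**What to change.** - Reconcile three things: the AMPS time in Table 2, the 30-minute interval (section 5.1 design text, Study-Days 2 and 3, and section 5.5), and the stated lengths of Study-Days 2 to 4. Say whether the interval runs from start to start or from end to start, and which tests the 1.0 h entry covers. Which figure is correct is for the investigators to settle.
- Record the clock time of iTBS and the start of every ImE and PE test.
- In section 5.6, define time in the ImE trend models as actual minutes since iTBS.
- Include the randomised ImE assignment as a covariate in the B1 and B3 contrasts, stating that this is for precision. One indicator serves both days, because the Day 3 test is the alternate of the Day 2 test.

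The cost is wording and time stamps. No tests, visits or participants are added.
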